### ***Data collection:***

The majority of data will be collected through face-to-face interview. A research assistant will read the questions to the participants while they read along from their own copies of the measures to maximize participant comprehension. If participants are unable or unwilling to attend a follow-up appointment at our Rutgers RWJMS offices, a research assistant will meet the participant off-site, in a public location agreeable to the participant such as a local public library. If off-site appointments are also impossible, we will conduct telephone interviews. Data will be stored at the Division of Addiction Psychiatry; [name]. Only the IRB-approved research team will have access to the research data.

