***1.2 Hypotheses***

1. We hypothesize that at least 80% of participants will rate the intervention as “easy to understand” and “helpful” on a post-intervention exit interview questionnaire.
2. We hypothesize that smokers with schizophrenia receiving our PTSC-S intervention will demonstrate cognitive and behavioral increases in task persistence from baseline to follow-up.

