### **3.3 Sample Size Justification**

26 participants will be enrolled.

We will enroll 26 smokers from the local area. We will collect demographic data that will allow us to compare this sample to the general population of smokers. This is a non-randomized, pilot, feasibility study so a power analysis is not applicable to this study design.

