## ***7. Statistical Analysis***

We will review all data quarterly.

To address hypothesis 1 that participants will rate the PTSC-S as “easy to understand” and “helpful” during a post-intervention exit interview, we will do the following:

- a) Calculate the percentage of participants who rate the intervention as “easy to understand” and “helpful” and test whether this percentage exceeds 80% using a one-sample test of binomial proportion (Rosner, 2010)
- b) Explore which participant characteristics tend to be associated with positive or negative views of this intervention, by examining bivariate association (e.g., chi-square test for discrete categorical characteristics and two-sample t-test for continuous measurements) and logistic regression analysis

To address hypothesis 2 that smokers with schizophrenia receiving our PTSC-S intervention will demonstrate cognitive and behavioral increases in task persistence (measured by mirror tracing, breath-holding, 2-item persistence self-report, Sustained Attention Test, and Thoughts About Smoking Questionnaire), we will do the following:

- a) Calculate and plot summary statistics to explore the cross-sectional and longitudinal distributions of persistence scores
- b) Use paired t-tests to probe for changes in task persistence from baseline to end-of-counseling (session 8), followed by mixed model analysis with persistence scores as the dependent variable and time as the independent variable
- c) Construct linear contrasts to evaluate changes in persistence scores from baseline to end-of-counseling (session 8). If the normality assumption is violated, we will apply the necessary variable transformations

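### Hypothesis 1's ease and helpfulness ratings have no stated private response mode, so courtesy answers can inflate the single-arm percentage compared with 80%

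*Combined protocol and SAP*

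**What the plan says.** Section 1.2 predicts that "at least 80% of participants will rate the intervention as" easy to understand and helpful, and places those ratings "on a post-intervention exit interview questionnaire". Section 7 says to "test whether this percentage exceeds 80% using a one-sample test of binomial proportion". Section 3.3 states that "26 participants will be enrolled" and that "a power analysis is not applicable to this study design". The study is open and non-randomized.

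On mode of collection, Section 6 (Data collection) says "The majority of data will be collected through face-to-face interview. A research assistant will read the questions to the participants", who follow on their own copies; the reason given is comprehension. A participant who cannot or will not come to the office is met elsewhere by a research assistant or, failing that, interviewed by telephone. The Exit interview row of the table in Section 4.2 gives no mode of its own.

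The data-management text in Section 6 has completed data brought to the principal investigator within a day, filed by participant number, and opened only for coding, entry or audit. The limitations paragraph mentions sample size and generalizability, but not response bias.

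**The concern.** Hypothesis 1 is the only hypothesis with a numeric benchmark, and it rests on stated approval of the treatment. If the default mode applies, participants give that approval in front of a member of the study team. A research assistant also obtains consent, runs the baseline battery and gives the depression measure at each session, so the listener may well be someone they know. Counseling and patches are free, and the manual is the team's own. Each of these favours a polite answer.

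In a two-arm trial much of such a pull would be shared between arms. In a single arm set against a fixed 80% it goes straight into the reported percentage. That percentage would serve as evidence of feasibility ahead of a randomized trial and in grant applications. Courtesy answers would also shrink the group with negative views that analysis 1(b) in Section 7 wants to describe, and with 26 participants that group is small already.

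**Working it through.** The plan states no power, significance level or sidedness for Hypothesis 1, so there is no figure of its own to reproduce.

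**Inputs.** From the documents: n = 26 (Section 3.3) and a benchmark of 80% (Sections 1.2 and 7). Assumed: all 26 give ratings, each participant counts as favourable or not, and one-sided alpha is 0.05. The true favourable rate p and the size of the courtesy effect are also assumed.

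**Step 1: the count that meets the benchmark.** 0.80 × 26 = 20.8, so 21 are needed; 21/26 = 80.8%.

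**Step 2: the count that passes the test.** Exact one-sided p = P(X ≥ r) with X ~ Binomial(26, 0.80):

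- r = 24: 0.0841
- r = 25: 0.0227

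So 25/26 (96.2%) is needed, and the same holds at one-sided 0.025. The normal approximation at one-sided 0.05 (critical value 1.645) agrees. Without continuity correction, 24/26 gives z = 1.569 and 25/26 gives 2.059; with correction, 1.324 and 1.814.

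**Step 3: a single case.** A true count of 20/26 (76.9%) needs 1 courtesy answer to reach 21/26. It needs 5 to reach 25/26.

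**Step 4: a 10-point lift.** Exact binomial, n = 26:

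| True → reported rate | P(X ≥ 21) | P(X ≥ 25) |
|---|---|---|
| 75% → 85% | 0.337 → 0.815 | 0.005 → 0.082 |
| 70% → 80% | 0.163 → 0.577 | 0.001 → 0.023 |

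**Step 5: range.** Let c be the share of non-favourable participants who answer favourably out of courtesy. Reported rate = p + (1 − p)c. A 10-point lift means c = 0.10/0.25 = 0.40 at p = 0.75 and c = 0.10/0.30 = 0.33 at p = 0.70. Other values:

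| p | c | Reported rate | P(X ≥ 21) | P(X ≥ 25) |
|---|---|---|---|---|
| 0.70 | 0 | 0.70 | 0.163 | 0.001 |
| 0.70 | 0.25 | 0.775 | 0.452 | 0.011 |
| 0.70 | 0.50 | 0.85 | 0.815 | 0.082 |
| 0.75 | 0 | 0.75 | 0.337 | 0.005 |
| 0.75 | 0.25 | 0.8125 | 0.641 | 0.032 |
| 0.75 | 0.50 | 0.875 | 0.903 | 0.146 |

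The descriptive benchmark is sensitive to modest courtesy effects. The formal test is much less so.

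**The case against.** **Mode is inferred.** Section 6 speaks of most of the data and does not name the exit interview. It says the assistant reads the items, not that answers are spoken, and Section 1.2 calls the instrument a questionnaire. A reader might infer that staff are known to take these ratings aloud; the documents do not say so. This stands, and it limits the point to an unspecified mode under a staff-run default. Nothing in the plan points to a private mode either.

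**The therapist is not the named reader.** Section 3 separates the research assistant (carbon monoxide readings at baseline and follow-up) from the therapist (readings at counseling sessions), and Section 6 names the assistant. Files carry only a participant number and access is restricted. These are real partial safeguards. They do not make the answer private, and nothing expressly keeps individual ratings from the therapist.

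**The lift is hypothetical.** No document gives an effect of interview mode, and gratitude for free treatment could persist on a private form that still carries an ID. This stands: private marking reduces the bias but cannot be assumed to remove it.

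**The stakes are modest.** No rule ties Hypothesis 1 to starting a later trial, Section 6 describes a mainly descriptive analysis, and 1(b) is exploratory. This also stands. But in a mainly descriptive analysis the observed percentage is what readers will use, and that is the quantity most exposed.

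**Conclusion.** The point holds in limited form. The plan gives no private response mode for the two ratings that decide Hypothesis 1, and its default and fallback modes are staff-run. Any courtesy effect would push the single-arm percentage upward with nothing to offset it. With all 26 rated and an assumed 10-point lift, the chance of meeting the 80% benchmark as worded in Section 1.2 rises from 34% to 82% (true rate 75%) or from 16% to 58% (true rate 70%).

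A reader might go on to infer that courtesy answers would readily carry the Section 7 test. They would not at this size of lift: the test needs 25/26 at the assumed alpha, and its chance of success rises only to 8.2% or 2.3%. The concern is therefore bias in a reported percentage, not a likely false-positive test, and it is worth correcting because the correction is nearly free.

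**What to change.** In Section 6 (Data collection) and in the Exit interview row of the Section 4.2 table, make these two items an exception to interview collection:

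- The research assistant may read each item aloud, which keeps the comprehension support. The participant marks their own copy out of staff sight and returns it in a sealed envelope labelled by ID, so that linkage for analysis 1(b) is kept.
- The therapist is absent and is not shown individual ratings, and the participant is told this beforehand.
- Where the interview is by telephone, the form is mailed back. Otherwise the mode is recorded and the percentage reported with and without telephone ratings.
- Open-ended exit questions can stay as an interview.
- Residual response bias is added to the limitations paragraph.

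If private completion is already intended, the same text records it.

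The cost is one form and an envelope; participants already hold their own copies. The downsides are a possibly slightly less favourable percentage and the occasional unmarked item. The latter matters at this size: 20/25 is exactly 80.0%, which meets the Section 1.2 wording but does not exceed 80% as Section 7 asks.

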### ***Data entry, editing and management, including handling of data collection forms, different versions of data, and data storage and disposition:***

To reduce the risk of violating confidentiality, several steps will be taken. Only IRB approved members of the research team will have access to the data. The research staff collecting the data will bring the data to the PI within 24 hours of it being collected (data are collected on secure laptops and/or in file folders identified only by participant ID number). The research team shares the same office space at [name]. Data will only be accessed when coded, entered, or audited. The PI will maintain responsibility for safe data storage. All data will be stored in locked cabinets within locked rooms in the Division of Addiction Psychiatry, [name].

All computer files will be kept on computers requiring login and complex passwords for entry, and all files with identifying information will have the extra protection of a password to open that individual file. The individual participant's personal information, including name and contact numbers, will be kept separate from their study data and linked only by a study number assigned by the PI. The master link between the study number and patient contact information will be destroyed once all data is collected and checked for accuracy. The confidential binder containing telephone screen forms will be shredded and properly discarded after 12 months of study completion. Participant names will not be used in any publications or papers derived from this study.

### ***Limitations of study:***

Because this is a pilot feasibility study, our sample size is relatively small and the generalizability of our findings should therefore be interpreted with caution.

## ***7. Statistical Analysis***

We will review all data quarterly.

To address hypothesis 1 that participants will rate the PTSC-S as “easy to understand” and “helpful” during a post-intervention exit interview, we will do the following:

- a) Calculate the percentage of participants who rate the intervention as “easy to understand” and “helpful” and test whether this percentage exceeds 80% using a one-sample test of binomial proportion (Rosner, 2010)
- b) Explore which participant characteristics tend to be associated with positive or negative views of this intervention, by examining bivariate association (e.g., chi-square test for discrete categorical characteristics and two-sample t-test for continuous measurements) and logistic regression analysis

To address hypothesis 2 that smokers with schizophrenia receiving our PTSC-S intervention will demonstrate cognitive and behavioral increases in task persistence (measured by mirror tracing, breath-holding, 2-item persistence self-report, Sustained Attention Test, and Thoughts About Smoking Questionnaire), we will do the following:

- a) Calculate and plot summary statistics to explore the cross-sectional and longitudinal distributions of persistence scores
- b) Use paired t-tests to probe for changes in task persistence from baseline to end-of-counseling (session 8), followed by mixed model analysis with persistence scores as the dependent variable and time as the independent variable
- c) Construct linear contrasts to evaluate changes in persistence scores from baseline to end-of-counseling (session 8). If the normality assumption is violated, we will apply the necessary variable transformations

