***2. Background and Significance***

We propose to modify a theory-based smoking cessation intervention (called Persistence-targeted smoking cessation; PTSC) to make it more feasible for treating smokers with schizophrenia. We will include 8 weekly individual counseling sessions and use of the nicotine patch for 10 weeks. We will provide counseling sessions and nicotine patches free of charge to research participants. We will test the feasibility of the intervention and its ability to influence persistence (measured as described in the table in section 4.2). We hope to develop a feasible psychosocial treatment for use in a later randomized controlled trial.

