## **6. Data Handling**

As this study is primarily a feasibility study, our data analysis plan will primarily comprise descriptive statistics such as mean (sd) sessions attended and percent of participants reporting 3-months post quit-date abstinence. We need to collect all of this data in order to demonstrate that our PTSC treatment manual is generalizable to a population of smokers with schizophrenia. We need to examine changes in relevant variables such as self-reported cigarette and medication use, withdrawal, smoking urges, and mechanisms of change in order to evaluate the efficacy of our treatment.

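### The exploratory logistic regression of positive versus negative views names no small-sample estimator, although the expected result leaves at most 5 negative raters among 26

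*Combined protocol and SAP*

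**What the plan says.** Section 1.2 sets the expectation: "We hypothesize that at least 80% of participants will rate the intervention as" easy to understand and helpful. Section 3.3 fixes the sample: "26 participants will be enrolled", with no power calculation.

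Section 7 then plans two steps for hypothesis 1. Item a is to "test whether this percentage exceeds 80% using a one-sample test of binomial proportion"; neither the significance level nor the sidedness is given. Item b is to "Explore which participant characteristics tend to be associated with positive or negative views of this intervention", by bivariate association (chi-square and t-test are given as examples) and by logistic regression: "two-sample t-test for continuous measurements) and logistic regression analysis". The regression stands outside the bracket of examples, so it is a planned method. No penalised or exact version and no covariate list is given.

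The paragraph on limitations says that "our sample size is relatively small and the generalizability of our findings should therefore be interpreted with caution". That concerns generalizability, not whether a model can be fitted. Section 6 describes the plan as mainly descriptive ("our data analysis plan will primarily comprise descriptive statistics").

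**The concern.** A logistic model takes its information from the rarer outcome. Here that is the negative view, and the better the treatment is received, the fewer negative raters there are. When one level of a binary characteristic has no negative raters, the maximum-likelihood odds ratio is infinite. Ordinary software then prints an arbitrary large coefficient with a huge standard error. Short of that point, the estimate is biased away from the null.

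Item b is where the study would learn who dislikes the treatment, and the pilot is meant to feed a later trial ("We hope to develop a feasible psychosocial treatment for use in a later randomized controlled trial", section 2). An odds ratio that is an artefact of the fitting algorithm would be a poor thing to carry forward.

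**Working it through.** The plan gives N = 26 without a calculation, so there is no planned figure to reproduce.

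**Inputs.** N = 26 (section 3.3); favourable rate at least 80% (section 1.2). Assumed: all 26 complete the exit interview, a view is scored yes/no, and the test in item a uses 0.05.

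**1. Number of negative raters.** 21/26 = 80.8% meets 80%; 20/26 = 76.9% does not. The maximum is 26 − 21 = 5. With fewer exit interviews it is 4 at n = 24, 22 or 20, and 3 at n = 18.

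**2. If the test in item a rejects 80%.** Exact: P(X ≥ 24 | 26, 0.8) = 0.0841 and P(X ≥ 25) = 0.0227 (doubled, 0.0453). Normal approximation: z = (x/26 − 0.8)/√(0.16/26) = 1.569 at x = 24 (one-sided p = 0.058) and 2.059 at x = 25 (one-sided 0.020, two-sided 0.039). All four versions need 25/26, which leaves at most 1 negative rater.

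**3. Chance of no finite odds ratio, given k negatives.** For a binary characteristic with groups of m and 26 − m and no association, the chance that all negatives fall in one group is [C(m,k) + C(26−m,k)]/C(26,k). Once k reaches the size of a group, terms for a group with no positive raters are added. For m = 13 and k = 5: 2 × 1287/65780 = 0.039.

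| Negatives k | 13/13 | 8/18 | 5/21 |
|---|---|---|---|
| 5 | 0.039 | 0.131 | 0.309 |
| 4 | 0.096 | 0.209 | 0.401 |
| 3 | 0.220 | 0.335 | 0.515 |
| 2 | 0.480 | 0.557 | 0.677 |
| 1 | 1.000 | 1.000 | 1.000 |

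**4. Averaged over k.** With k ~ Binomial(26, 1 − p), all k ≥ 1 included (so also 6 or more):

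| True favourable rate p | 13/13 | 8/18 | 5/21 |
|---|---|---|---|
| 80% | 0.104 | 0.180 | 0.332 |
| 90% | 0.405 | 0.483 | 0.610 |

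Part of this comes from trials with exactly one negative, where no method helps. At 90% that share is 26 × 0.1 × 0.9^25/(1 − 0.9^26) = 0.187/0.935 = 0.200 of the 0.405 on a 13/13 split. At 80% it is 0.0196/0.997 = 0.020 of the 0.104.

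**5. How firm is the limit of 5?** P(6 or more negatives) = 0.42 if the true rate is exactly 80%, and 1 − 0.960 = 0.04 at 90%.

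**6. What the output looks like.** Take 5 v 0 negatives on a 13/13 split.

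| Method | Result |
|---|---|
| Maximum likelihood | log odds ratio 22.1, SE 13,367, Wald p = 0.999 |
| Likelihood-ratio test, same model | p = 0.004 |
| Uncorrected chi-square | p = 0.013 |
| Fisher | p = 0.039 |
| Firth | odds ratio (5.5 × 13.5)/(0.5 × 8.5) = 17.5, profile 95% CI 1.6 to about 2400, p = 0.014 |

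**7. Continuous characteristics.** A single normal covariate was separated in 0.0005 (80%) and 0.016 (90%) of simulated trials, so infinite estimates are rare there. Bias remains. With 1 to 5 negatives and a true log odds ratio of 0.693 per SD, maximum likelihood (separated fits excluded) averaged 0.98 (SD 1.35) and Firth 0.73 (SD 0.76).

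**The case against.** The strongest reply is that the plan already has a safeguard. Chi-square is named as an example of the bivariate tests in the same sentence, and on the 5 v 0 pattern it gives p = 0.013; the likelihood-ratio test from the ordinary model gives 0.004. A reader might infer from the Wald p = 0.999 that the planned analysis would hide the clearest pattern in the data. The documents do not support that: they never say a Wald test would be used, and the bivariate result stands beside it. This part of the objection holds. What remains is the estimate and its interval, which chi-square does not supply.

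Second, Firth fitting creates no information. With 1 v 0 negatives it gives an odds ratio of 3.2, interval 0.16 to about 490, p = 0.45. Nor is its inference uniformly better: with 4 negatives on a 13/13 split it rejects a true null 9.6% of the time, because it calls 4 v 0 significant where Fisher gives p = 0.096. Both facts stand. They are why the proposed text fits no model with a single negative rater.

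Third, 80% is a hypothesis, and the scoring is not defined. If ease of understanding and helpfulness are scored separately, the limit of 5 applies to each. If each meets 80% but a view counts as positive only when both are, up to 5 + 5 = 10 participants could be negative. This also stands, and it makes the limit conditional.

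Finally, an analyst could adapt on seeing the data. That would be a choice of estimator made after the result, which one sentence now avoids.

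**Conclusion.** The point holds as an inexpensive improvement to one exploratory item. In the scenario that the plan expects, ordinary logistic regression gives no finite odds ratio for a binary characteristic in about 10% to 33% of trials at a true rate of 80%, and 41% to 61% at 90%. This assumes no association, at least 1 negative rater, splits from 13/13 to 5/21, complete exit interviews and yes/no scoring. If the test in item a succeeds at 0.05 and one negative rater remains, it happens for every binary characteristic.

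Two stronger readings should be resisted. One is that the regression cannot be done: 6 or more negatives remain quite possible at 80%, and most single-characteristic fits at that rate are finite. The other is that the chi-square test must be replaced, or the regression limited to one covariate at a time. Chi-square is only an example in the plan. Both changes are trade-offs: the first between error rate and conservatism, the second between stability and adjusted estimates.

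The test in item a, hypothesis 2 and the sample size are unaffected.

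**What to change.** In section 7, hypothesis 1, item b, write: *Logistic regression will be fitted by Firth-penalised likelihood with profile-likelihood 95% CIs and reported as exploratory, with the number of negative raters. If there are no negative raters or only one, results will be described and no model fitted.*

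The cost is two sentences and standard software, with no new data. The downside is that estimates become finite but stay very imprecise, and coverage for a given number of negatives can fall below 95%, as the 9.6% false-rejection case shows. The report should therefore present the intervals as a guide to how little is known, not as tests.

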***1.1 Objectives***

We will demonstrate that our new treatment “Persistence Targeted Smoking Cessation in Schizophrenia (PTSC-S)” is feasible for treating smokers with schizophrenia and that it increases their task persistence.

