### **3. Research Design and Methods**

We will conduct an open trial (N=26) of our 8-session, weekly, individual treatment, (Persistence Targeted Smoking Cessation for Schizophrenia (PTSC-S)). The purpose of this open trial will be to “begin to demonstrate that the intervention alters the targeted mechanism (thus providing an initial proof of principle).” We will measure task persistence via behavioral and cognitive measures administered in counterbalanced order at baseline, after session 3, and at one- and three-months post-quit date. By assessing task persistence at multiple follow-up points, we will be able to examine how many sessions are required to produce an effect (i.e., effect of treatment “dose”).

A trained research assistant (who will receive weekly and as-needed supervision from the principal investigator) will pre-screen potential participants on the phone, followed by obtaining informed consent and administering the baseline assessment battery (see Assessment Measures table below). We will divide the baseline assessment battery into two sessions to minimize participant fatigue. Each baseline assessment session will last approximately 90 minutes. We will then provide free, weekly individual counseling sessions for 8 weeks and 10-weeks’ worth of the nicotine transdermal patch (an FDA-approved smoking cessation product available over the counter). All sessions will be audio recorded for treatment integrity and supervision.

Questionnaires that are commonly used in tobacco dependence treatment studies will be used in the current study. Women of childbearing age will take a pregnancy test to rule out pregnancy. Carbon monoxide (CO) levels (also commonly collected in tobacco dependence treatment studies) will be assessed with a carbon monoxide monitor and CO reading in parts per million (ppm) will be recorded. The carbon monoxide monitor used will be the *Bedfont Scientific Ltd. Micro+ Smokerlyzer*. The Micro+ Smokerlyzer is a hand-held, battery powered instrument which uses electrochemical technology to sample the gas and a microprocessor to convert the output from the sensor to a carbon monoxide (CO) concentration. The result and menus are displayed on a color LCD and an accompanying buzzer sounds in response to the CO level. The instrument is controlled using a touch screen operation and has a USB link to a computer to download readings.

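### Does hypothesis 2 need a written rule for how many of the five persistence measures must rise, and for whether the t-test or the mixed model decides?

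*Combined protocol and SAP*

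**What the plan says.** Section 1.2 states that participants "will demonstrate cognitive and behavioral increases in task persistence from baseline to follow-up". Section 7 repeats the aim and lists what will be analysed: "measured by mirror tracing, breath-holding, 2-item persistence self-report, Sustained Attention Test, and Thoughts About Smoking Questionnaire". Two analyses of the same change follow. Item (b) reads "Use paired t-tests to probe for changes in task persistence from baseline to end-of-counseling (session 8), followed by mixed model analysis", with time as the independent variable. Item (c) reads "Construct linear contrasts to evaluate changes in persistence scores from baseline to end-of-counseling (session 8". Alpha, a primary measure, a multiplicity adjustment, the model's covariance and the handling of missing session 8 values are not given.

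Other sections set the weight of this analysis. Section 1.1 promises to show that the treatment "is feasible for treating smokers with schizophrenia and that it increases their task persistence". Section 3 is more modest: the trial is to "begin to demonstrate that the intervention alters the targeted mechanism". Section 6 says "our data analysis plan will primarily comprise descriptive statistics". Section 3.3 sets the sample at 26 and declares a power analysis not applicable. The table in Section 4.2 also places the TCI persistence scale and the Distress Tolerance Scale under task persistence, but Section 7 does not list them for hypothesis 2.

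**The concern.** Five measures and two analyses give up to ten looks at one question, with no stated rule for turning the results into a conclusion. Read against the confident wording of Section 1.1, one nominally significant rise out of five could be presented as showing that the treatment increases task persistence. An author could also choose whichever of the t-test and the contrast looked better. The phrase about cognitive and behavioral increases hints that both types must rise. Section 3 uses the same split ("We will measure task persistence via behavioral and cognitive measures administered in counterbalanced order"), but the five measures are never assigned to one type or the other. Section 8 foresees publications and grant applications, so an overstated result could travel.

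**Working it through.** The plan states no error rate or power for hypothesis 2, so there is no figure of its own to reproduce.

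**Inputs from the document:** five measures (Section 7); 26 participants (Section 3.3); an increase is the direction of interest (Section 1.2).

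**Assumptions, not in the document:** two-sided 0.05 per test, so 0.025 in the upward direction; a common correlation between the five change scores; complete data unless stated.

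**Step 1: any one of five counts, nothing truly changes.** With independent measures the chance of at least one false increase is 1 − 0.975^5 = 1 − 0.881 = 11.9%. For correlated measures, paired t-tests were simulated at n = 26 (100,000 runs per setting); see the table.

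**Step 2: both types must rise, nothing truly changes.** Splitting the five into two and three (the split is an assumption), independence gives (1 − 0.975²)(1 − 0.975³) = 0.0494 × 0.0731 = 0.4%. With one named measure of each type it is 0.025² = 0.06%.

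| Correlation | Any one of five | At least one of each type | One named measure of each type |
|---|---|---|---|
| 0 | 11.9% | 0.4% | 0.06% |
| 0.3 | 10.6% | 1.0% | 0.2% |
| 0.5 | 9.2% | 1.6% | 0.4% |
| 0.7 | 7.6% | 2.2% | 0.8% |
| 0.9 | 5.2% | 2.6% | 1.5% |

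**Step 3: one type truly rises and the other does not.** A false claim that both rose can then be as likely as any false increase in the null type. Independent measures give 1 − 0.975² = 4.9% for two null measures and 1 − 0.975³ = 7.3% for three. At correlation 0.5 these are about 4.5% and 6.3%; at 0.7, about 4.2% and 5.6%. A both-types rule therefore does not by itself guarantee 2.5%; naming one measure of each type does.

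**Step 4: either analysis may count.** With a constant correlation over four visits, and a model that assumes it, one measure goes from 2.5% to about 3.0%. Any one of five goes from 11.9% to 14.3% (correlation between measures 0), 10.4% to 12.4% (0.3) and 9.3% to 10.8% (0.5). With an unstructured covariance and complete data the contrast reproduces the paired t-test, so nothing is added. If the correlation decays over visits but the model holds it constant, the model alone gives about 3.5 to 3.8% per measure. That is an error in the covariance choice and would arise with a single measure too.

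**Step 5: what plain reporting provides, and what adjustment costs.** In units of the SD of change, the 95% interval half-width is t/√n: 2.060/√26 = 0.40 at n = 26 and 2.110/√18 = 0.50 at n = 18. The change detectable with 80% power is 0.57 SD at alpha 0.05. Bonferroni over five measures (alpha 0.01) raises this to 0.72 SD and cuts power at 0.57 SD to 56%.

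**The case for a change.** The strongest case for a change is that the inferential language is in the plan: an objective worded as a demonstration, a directional hypothesis, and tests assigned to it. The limitations paragraph in Section 6 warns about sample size and generalizability, not about multiple measures. A rule is credible only if fixed before the data are seen, and Section 7 has the team reviewing data quarterly. The wording would cost nothing to add, and even the natural both-types reading leaves a false rate of about 4 to 7% when only one type improves and no measures are named.

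Most of that is factually right, and it stands as a caution to whoever writes the report: no single nominal p-value among five should be read as establishing hypothesis 2. It does not show that the plan as written yields a wrong result. The larger figures need a decision rule the plan never adopts. A fuller specification would also bring debatable choices of its own. An unstructured covariance over four visits needs 4 × 5/2 = 10 parameters per measure from at most 26 people, and its small-sample correction was not included in the simulations. In an illustrative setting with 31% missing session 8 values, where drop-out depends on the unobserved session 8 score, that model without the correction was more biased than the paired t-test (+0.18 against +0.13 SD) and gave more false increases (12.5% against 7.7% per measure).

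**Conclusion.** The gap is genuine, but it is an unwritten detail and no change to the plan follows. Three features of the document limit what it can do. Hypothesis 2 asks for increases of both types, which argues against counting any one of five. Section 7 uses the t-tests to probe and puts the model and its contrasts after them, so the main analysis can be inferred. And the trial is a 26-person, uncontrolled, primarily descriptive pilot in which no decision is tied to a hypothesis 2 p-value; the comparison with an established treatment is left to a later randomized trial. The measures in the Section 4.2 table that Section 7 omits lie outside hypothesis 2 by that omission.

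A sensible analyst will report all five measures together with 95% intervals, about ±0.40 SD of change at full retention, treat the contrast as the main result and the t-test as preliminary, and describe the pattern. That takes no amendment.

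On the least favourable reading of the number of measures, the false-increase rate is about 7.5 to 12% against 2.5% for one test, or about 11 to 14% if either analysis may also count (constant visit correlation, correlation between measures 0.5 down to 0). These figures rest on two-sided 0.05, 26 participants and an any-one-of-five rule, none of which Section 7 sets as a decision rule.

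One separate matter is not settled here: Section 3 and the Section 4.2 table give different assessment times, and Section 1.2 speaks of follow-up where Section 7 names session 8.
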